11.1.3. Methods for Evaluation of Measurable Disease

All measurements should be taken and recorded in metric notation using a ruler or calipers. All baseline evaluations should be performed as closely as possible to the beginning of treatment and never more than 4 weeks before the beginning of the treatment.

The same method of assessment and the same technique should be used to characterize each identified and reported lesion at baseline and during follow-up. Imaging-based evaluation is preferred to evaluation by clinical examination unless the lesion(s) being followed cannot be imaged but are assessable by clinical exam.

Clinical lesions Clinical lesions will only be considered measurable when they are superficial (e.g., skin nodules and palpable lymph nodes) and ≤ 10 mm diameter as assessed using calipers (e.g., skin nodules). In the case of skin lesions, documentation by color photography, including a ruler to estimate the size of the lesion, is recommended.

Chest x-ray Lesions on chest x-ray are acceptable as measurable lesions when they are clearly defined and surrounded by aerated lung. However, CT is preferable.

Conventional CT and MRI This guideline has defined measurability of lesions on CT scan based on the assumption that CT slice thickness is 5 mm or less. If CT scans have slice thickness greater than 5 mm, the minimum size for a measurable lesion should be twice the slice thickness. MRI is also acceptable in certain situations (e.g. for body scans).

Use of MRI remains a complex issue. MRI has excellent contrast, spatial, and temporal resolution; however, there are many image acquisition variables involved in MRI, which greatly impact image quality, lesion conspicuity, and measurement. Furthermore, the availability of MRI is variable globally. As with CT, if an MRI is performed, the technical specifications of the scanning sequences used should be optimized for the evaluation of the type and site of disease. Furthermore, as with CT, the modality used at follow-up should be the same as was used at baseline and the lesions should be measured/assessed on the same pulse sequence. It is beyond the scope of the RECIST guidelines to prescribe specific MRI pulse sequence parameters for all scanners, body parts, and diseases. Ideally, the same type of scanner should be used and the image acquisition protocol should be followed as closely as possible to prior scans. Body scans should be performed with breath-hold scanning techniques, if possible.

PET-CT At present, the low dose or attenuation correction CT portion of a combined PET-CT is not always of optimal diagnostic CT quality for use with RECIST measurements. However, if the site can document that the CT performed as part of a PET-CT is of identical diagnostic quality to a diagnostic CT (with IV and oral contrast), then the CT portion of the PET-CT can be used for RECIST measurements and can be used interchangeably with conventional CT in accurately measuring cancer lesions over time. Note, however, that the PET portion of the CT introduces additional data which may bias an investigator if it is not routinely or serially performed.

Ultrasound Ultrasound is not useful in assessment of lesion size and should not be used as a method of measurement. Ultrasound examinations cannot be reproduced in their entirety for independent review at a later date and, because they are operator dependent, it cannot be guaranteed that the same technique and measurements will be taken from one assessment to the next. If new lesions are identified by ultrasound in the course of the study, confirmation by CT or MRI is advised. If there is concern about radiation exposure at CT, MRI may be used instead of CT in selected instances.

Endoscopy, Laparoscopy The utilization of these techniques for objective tumor evaluation is not advised. However, such techniques may be useful to confirm complete pathological response when biopsies are obtained or to determine relapse in trials where recurrence following complete response (CR) or surgical resection is an endpoint.

Tumor markers Tumor markers alone cannot be used to assess response. If markers are initially above the upper normal limit, they must normalize for a patient to be considered in complete clinical response. Specific guidelines for both CA-125 response (in recurrent ovarian cancer) and PSA response (in recurrent prostate cancer) have been published [*JNCI* 96:487-488, 2004; *J Clin Oncol* 17, 3461-3467, 1999; *J Clin Oncol* 26:1148-1159, 2008]. In

addition, the Gynecologic Cancer Intergroup has developed CA-125 progression criteria which are to be integrated with objective tumor assessment for use in first-line trials in ovarian cancer [*JNCI* 92:1534-1535, 2000].

Cytology, Histology These techniques can be used to differentiate between partial responses (PR) and complete responses (CR) in rare cases (e.g., residual lesions in tumor types, such as germ cell tumors, where known residual benign tumors can remain).

The cytological confirmation of the neoplastic origin of any effusion that appears or worsens during treatment when the measurable tumor has met criteria for response or stable disease is mandatory to differentiate between response or stable disease (an effusion may be a side effect of the treatment) and progressive disease.

FDG-PET While FDG-PET response assessments need additional study, it is sometimes reasonable to incorporate the use of FDG-PET scanning to complement CT scanning in assessment of progression (particularly possible 'new' disease). New lesions on the basis of FDG-PET imaging can be identified according to the following algorithm:

- a. Negative FDG-PET at baseline, with a positive FDG-PET at follow-up is a sign of PD based on a new lesion.
- b. No FDG-PET at baseline and a positive FDG-PET at follow-up: If the positive FDG-PET at follow-up corresponds to a new site of disease confirmed by CT, this is PD. If the positive FDG-PET at follow-up is not confirmed as a new site of disease on CT, additional follow-up CT scans are needed to determine if there is truly progression occurring at that site (if so, the date of PD will be the date of the initial abnormal FDG-PET scan). If the positive FDG-PET at follow-up corresponds to a pre-existing site of disease on CT that is not progressing on the basis of the anatomic images, this is not PD.
- c. FDG-PET may be used to upgrade a response to a CR in a manner similar to a biopsy in cases where a residual radiographic abnormality is thought to represent fibrosis or scarring. The use of FDG-PET in this circumstance should be prospectively described in the protocol and supported by disease-specific medical literature for the indication. However, it must be acknowledged that both approaches may lead to false positive CR due to limitations of FDG-PET and biopsy resolution/sensitivity.

Note: A 'positive' FDG-PET scan lesion means one which is FDG avid with an uptake greater than twice that of the surrounding tissue on the attenuation corrected image.

11.1.4. Response Criteria

11.1.4.1. Evaluation of Target Lesions

Complete Response (CR): Disappearance of all target lesions. Any pathological lymph nodes (whether target or non-target) must have reduction in short axis to <10 mm.

Partial Response (PR):	At least a 30% decrease in the sum of the diameters of target lesions, taking as reference the baseline sum diameters
Progressive Disease (PD):	At least a 20% increase in the sum of the diameters of target lesions, taking as reference the smallest sum on study (this includes the baseline sum if that is the smallest on study). In addition to the relative increase of 20%, the sum must also demonstrate an absolute increase of at least 5 mm. (Note: the appearance of one or more new lesions is also considered progressions).
Stable Disease (SD):	Neither sufficient shrinkage to qualify for PR nor sufficient increase to qualify for PD, taking as reference the smallest sum diameters while on study

11.1.4.2. Evaluation of Non-Target Lesions

Complete Response (CR): Disappearance of all non-target lesions and normalization of tumor marker level. All lymph nodes must be non-pathological in size (<10 mm short axis)

Note: If tumor markers are initially above the upper normal limit, they must normalize for a patient to be considered in complete clinical response.

Non-CR/Non-PD: Persistence of one or more non-target lesion(s) and/or maintenance of tumor marker level above the normal limits

Progressive Disease (PD): Appearance of one or more new lesions and/or *unequivocal progression* of existing non-target lesions. *Unequivocal progression* should not normally trump target lesion status. It must be representative of overall disease status change, not a single lesion increase.

Although a clear progression of “non-target” lesions only is exceptional, the opinion of the treating physician should prevail in such circumstances, and the progression status should be confirmed at a later time by the review panel (or Principal Investigator).

11.1.4.3. Evaluation of Best Overall Response

The best overall response is the best response recorded from the start of the treatment until disease progression/recurrence (taking as reference for progressive disease the smallest measurements recorded since the treatment started). The patient's best response assignment will depend on the achievement of both measurement and confirmation criteria.

For Patients with Measurable Disease (i.e., Target Disease)

Target Lesions	Non-Target Lesions	New Lesions	Overall Response	Best Overall Response when Confirmation is Required*
CR	CR	No	CR	≥4 wks. Confirmation**
CR	Non-CR/Non-PD	No	PR	≥4 wks. Confirmation**
CR	Not evaluated	No	PR	
PR	Non-CR/Non-PD/not evaluated	No	PR	
SD	Non-CR/Non-PD/not evaluated	No	SD	documented at least once ≥4 wks. from baseline**
PD	Any	Yes or No	PD	no prior SD, PR or CR
Any	PD***	Yes or No	PD	
Any	Any	Yes	PD	

* See RECIST 1.1 manuscript for further details on what is evidence of a new lesion. ** Only for non-randomized trials with response as primary endpoint. *** In exceptional circumstances, unequivocal progression in non-target lesions may be accepted as disease progression.
 
Note: Patients with a global deterioration of health status requiring discontinuation of treatment without objective evidence of disease progression at that time should be reported as “symptomatic deterioration.” Every effort should be made to document the objective progression even after discontinuation of treatment.
				

For Patients with Non-Measurable Disease (i.e., Non-Target Disease)

Non-Target Lesions	New Lesions	Overall Response
CR	No	CR
Non-CR/non-PD	No	Non-CR/non-PD*
Not all evaluated	No	not evaluated
Unequivocal PD	Yes or No	PD
Any	Yes	PD
* 'Non-CR/non-PD' is preferred over 'stable disease' for non-target disease since SD is increasingly used as an endpoint for assessment of efficacy in some trials so to assign this category when no lesions can be measured is not advised		

11.1.5. Duration of Response

Duration of overall response: The duration of overall response is measured from the time measurement criteria are met for CR or PR (whichever is first recorded) until the first date that recurrent or progressive disease is objectively documented (taking as reference for progressive disease the smallest measurements recorded since the treatment started).

The duration of overall CR is measured from the time measurement criteria are first met for CR until the first date that progressive disease is objectively documented.

Duration of stable disease: Stable disease is measured from the start of the treatment until the criteria for progression are met, taking as reference the smallest measurements recorded since the treatment started, including the baseline measurements.

11.1.6. Progression-Free Survival

Progression free survival (PFS) is defined as the duration of time from start of treatment to time of progression or death of any cause.

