1.1.2. Secondary Objectives

- Determine the response rate of cediranib in combination with lenalidomide in patients with iodine refractory, unresectable DTC who have evidence of disease progression within 12 months of study enrollment.
- Determine the toxicity, duration of response, progression free survival, and overall survival in patients with DTC treated with cediranib plus lenalidomide.

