3.1.12. Females of childbearing potential (FCBP)[†] who receive cediranib alone must also have a negative initial and ongoing pregnancy tests as described above in 3.1.11. FCBP who receive cediranib alone must also commit to continued abstinence from heterosexual intercourse or begin TWO acceptable methods of birth control, one highly effective method and one additional effective method AT THE SAME TIME, at least 28 days before she starts taking cediranib. Men on cediranib alone must agree to use a latex condom during sexual contact with a FCBP even if they have had a successful vasectomy. All patients receiving cediranib alone must be counseled at a minimum of every 28 days about pregnancy precautions and risks of fetal exposure.

3.1.13. Ability to understand and the willingness to sign a written informed consent document.

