4. REGISTRATION PROCEDURES

4.1. General Guidelines

Eligible patients will be entered on study centrally at the University of Chicago by the Study Registrar. All sites should call the Study Registrar at **[contact]** or **[contact]**, to verify agent availability. The UC

Phase II Consortium Affiliate Forms are available on the University of Chicago Cancer Research Center website.

- <http://uccrc.uchicago.edu/current/home.html>
- Click on the **Staff Resources** link and scroll down to “UC Phase II Consortium Forms” section.

Except in very unusual circumstances, each participating institution will order DCTD-supplied agents directly from CTEP. Agents may be ordered by a participating site only after the initial IRB approval for the site has been forwarded by the Coordinating Center to the CTEP PIO ([contact]) except for Group studies. Eligible patients will be entered on study centrally at the University of Chicago by the Registrar. All sites should call the Registrar at [contact] to verify agent availability.

Following registration, patients should begin protocol treatment within 14 days. Issues that would cause treatment delays should be discussed with the Principal Investigator. If a patient does not receive protocol therapy following registration, the patient’s registration on the study may be canceled. The Registrar should be notified of cancellations as soon as possible.

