4.2. Registration Process

All patients must be registered with the University of Chicago Registrar at least 48 hours prior to the commencement of treatment. The following documents should be completed by the research nurse or data manager and faxed [contact] or emailed [contact] to the Registrar:

- Provider of information
- Treating Physician
- Patient name and hospital ID number
- Patient's zip code of residence
- Date & copy of signed informed consent
- Race, gender, date of birth of patient
- Diagnosis and date of initial diagnosis
- Prior therapy with a VEGF-pathway inhibitor (yes/no)
- ECOG performance status
- Complete **Phase II Consortium Affiliate Clinical Trial Patient Registration Form**
- Source documentation for eligibility and pre-study procedures

The research nurse or data manager at the participating site will then call [contact]) or e-mail [contact] to confirm all selection criteria listed in Section 4.0. To complete the registration process, the Coordinator will:

- Assign a patient study number
- Register the patient on the study
- Fax or e-mail the patient study number and dose to the participating site

Call the research nurse or data manager at the participating site and verbally confirm registration.

Each site must have two trained counselors available for counseling all patients receiving lenalidomide supplied by the Division of Cancer Treatment and Diagnosis. Trained counselors must complete training using the online program provided free by Celgene, the Lenalidomide Counseling Program (LCP). Registration for LCP is done by completing the form found in Appendix K and following the directions provided in the email notification. After the training is complete, the counselors must generate a training certificate and provide it to the PMB for documentation. Sites may not order lenalidomide until documentation for two trained counselors is provided to the appropriate office.

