5.4. Duration of Follow Up

Patients removed from study for unacceptable adverse events will be followed until resolution or stabilization of the adverse event. Unless the patient withdraws from the study, the subject will be followed until disease progression or death, whichever comes first.

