13. STATISTICAL CONSIDERATIONS

13.1. Study Design/Endpoints

13.1.1. Phase I.

The phase I trial will use a 3+3 design with the MTD defined as the highest dose level such that <2 of 6 patients experience dose-limiting toxicity.

13.1.2. Phase II.

There is no standard therapy for differentiated thyroid cancer that is refractory to radioactive iodine. The best studied agent in this disease, doxorubicin, has an estimated response rate of 10%. Although cediranib has not been studied in thyroid cancer, a phase II study of the VEGF inhibitor motesanib diphosphate showed a median progression-free survival (PFS) of 40 weeks. Because we hypothesize that combination therapy will be more effective than single agent treatment, we will randomize in a 1:2 ratio, which should enhance recruitment. The randomization will be stratified by prior therapy with a VEGF-pathway inhibitor (yes vs. no) and performance status (0-1 vs. 2)

The primary endpoint will be PFS, which will be compared between the two treatment arms using a stratified logrank test. To determine the sample size, we noted that the median PFS in 93 patients with radioiodine-resistant thyroid cancer treated with motesanib diphosphate²⁵ was 40 weeks. We therefore assume a median of 40 weeks for the cediranib alone arm. In order to have 85% power to detect a 75% improvement in the median to 70 weeks with combination therapy (hazard ratio [HR]=1.75), 110 patients will be required (36 randomized to cediranib and 74 to cediranib plus lenalidomide), based on a one-sided test at the $\alpha=0.10$ significance level. This calculation assumes 1 year of accrual (9 patients per month) and 1.5 years of additional follow-up for a total study duration of 2.5 years. Kaplan-Meier³⁰ curves will be generated for each treatment arm and the median PFS times estimated using the Brookmeyer and Crowley method³¹. In addition to the logrank test, PFS in the two groups will be analyzed by fitting a Cox³² proportional hazards regression model, adjusting for prior VEGF inhibitor use, performance status, and other baseline risk factors. The goodness of fit of the Cox model and the appropriate functional form for continuous covariates will be assessed using graphical techniques, including inspection of martingale residual plots.

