13.5. Reporting and Exclusions

13.5.1. **Evaluation of toxicity.** All patients (Phase I and II) will be evaluable for toxicity from the time of their first treatment with cediranib or cediranib plus lenalidomide.

13.5.2. **Evaluation of response.** All patients included in the study (Phase I and II) will be assessed for response to treatment, even if there are major protocol treatment deviations or if they are ineligible. Each patient will be assigned one of the following categories: 1) complete response, 2) partial response, 3) stable disease, 4) progressive disease, 5) early

death from malignant disease, 6) early death from toxicity, 7) early death because of other cause, or 9) unknown (not assessable, insufficient data).

All of the patients who met the eligibility criteria (with the possible exception of those who received no study medication) will be included in the main analysis of the response rate. Patients in response categories 4-9 will be considered to have a treatment failure (disease progression). Thus, an incorrect treatment schedule or drug administration will not result in exclusion from the analysis of the response rate.

All conclusions will be based on all eligible patients. Subanalyses may then be performed on the basis of a subset of patients, excluding those for whom major protocol deviations have been identified (e.g., early death due to other reasons, early discontinuation of treatment, major protocol violations, etc.). However, these subanalyses will not serve as the basis for drawing conclusions concerning treatment efficacy, and the reasons for excluding patients from the analysis will be clearly reported. Data will be reported to CTEP using CDUS -Complete.

REFERENCES

1. National Cancer Institute. Surveillance, Epidemiology, and End Results (SEER) Program. <http://seer.cancer.gov/> Accessed 2009.
2. American Cancer Society. www.cancer.org/docroot/home/. Accessed 2009.

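### Phase II PFS starts at first dose and no all-randomised analysis set is named, so non-starters or ineligible patients can leave the primary comparison

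*Combined protocol and SAP*

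**What the plan says.** - Section 2.1 describes Phase II as a two-arm, open-label, randomised trial. Section 13.1.2 states: "The primary endpoint will be PFS, which will be compared between the two treatment arms using a stratified logrank test". It also plans a Cox model. It names no analysis population for either. Its sample-size sentence speaks of 36 and 74 randomised patients.
- Section 11.1.6 gives one PFS definition for the whole protocol: "defined as the duration of time from start of treatment to time of progression or death of any cause".
- Section 13.5.2, titled for response evaluation but under the general heading on reporting and exclusions, states: "All conclusions will be based on all eligible patients". For the main response-rate analysis it also allows patients who took no study drug to be left out.
- Section 4.1 asks for treatment to begin within 14 days of registration. If no therapy is given, the patient's "registration on the study may be canceled".
- Section 4.2 collects both stratification factors at registration, and the coordinator then has to "Fax or e-mail the patient study number and dose to the participating site". It lists no randomisation step and no randomisation date.
- Section 5.4 states: "Unless the patient withdraws from the study, the subject will be followed until disease progression or death, whichever comes first".

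**The concern.** A randomised comparison is protected as long as everyone randomised is compared in the arm assigned. Here the time origin falls after randomisation, so the definition itself leaves a non-starter without an outcome. Ineligible patients may also be dropped if the 13.5.2 sentence is applied to PFS. In an open-label trial the arm is known before the first dose, so a decision not to start can depend on the arm. If loss is linked to both arm and prognosis, the logrank test no longer holds its error rate. The gap extends to overall survival, which 13.4.2 compares by methods similar to those for PFS. Without a fixed set, the population could also be settled after outcomes are known.

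**Working it through.** **1. The plan's own figure.** Inputs from 13.1.2: medians of 40 and 70 weeks (ratio 1.75), one-sided alpha 0.10, power 85%, 36 and 74 patients, 1 year of accrual and 1.5 years of further follow-up. Schoenfeld's formula, with allocation fraction p = 36/110 = 0.327:

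events = (1.2816 + 1.0364)² / [p(1−p)(ln 1.75)²] = 5.373 / (0.2202 × 0.3132) = 77.9, that is 78.

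The plan projects 80, which would give 85.7% power. Exponential PFS with uniform accrual and no dropout gives 29.9 + 47.4 = 77.3 expected events and 84.8% power. The design reproduces, and it uses all 110 randomised patients with no allowance for exclusions.

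**2. Equal exclusion from both arms.** The documents give no rates, so these are assumed.

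| Excluded | Events | Power |
|---|---|---|
| 0% | 77.3 | 84.8% |
| 2% | 75.7 | 84.2% |
| 5% | 73.4 | 83.4% |
| 10% | 69.5 | 81.8% |

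The cost is 84.8 − 84.2 = 0.6 to 84.8 − 81.8 = 3.0 points.

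**3. Error rate under selective loss.** Simulation of 40,000 trials per scenario: 36 versus 74 patients, exponential PFS with a 40-week median in both arms, accrual uniform over 52 weeks plus 78 weeks of follow-up, and an unstratified one-sided logrank test at 0.10 in favour of the combination. The Monte Carlo standard error is about 0.1 to 0.2 points. The weight is how many times as likely a patient who fails by week 8 is to be lost.

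| Patients lost | Weight | One-sided error |
|---|---|---|
| None | – | 10.7% |
| 3 from B, 3 from A, 1A+2B or 3A+6B | 1 (random) | 10.6-10.8% |
| 1A+2B or 3A+6B | 5 | 10.7-10.8% |
| 3 from B | 3 | 11.7% |
| 3 from B | 5 | 11.9% |
| 3 from A | 3 | 9.4% |
| 3 from A | 5 | 8.4% |
| 3 from B, all week-8 failures | bound | 15.5% |
| 3 from A, all week-8 failures | bound | 5.1% |

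The scenarios should be read against 10.7%, the simulated rate with nobody lost, and not against the nominal 10%.

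**4. How extreme the bounds are.** The probability of failing by week 8 is 1 − 0.5^(8/40) = 0.129, or about 9.6 of 74 patients. Three random losses would all be such failures with probability 0.129³ = 0.002.

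**5. A harsher illustration.** Suppose 2, 4 or 8 Arm B patients are lost, all from the 30% of that arm with the shortest PFS. In a separate 20,000-trial run the error rises from 10.9% to 13.6%, 16.5% or 24.3%. Nothing in the documents supports such a pattern.

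**The case against.** The strongest reply is that the exclusions are less open than they look. Several of its points stand.

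- *Reach of 13.5.2.* The eligible-patient sentence sits under response evaluation, so its application to PFS is an extension. That is true. But it speaks of all conclusions, the paragraph goes on to treatment efficacy, and no text exempts PFS.
- *Protections in 13.5.2.* All included patients, even ineligible ones, are assessed for response. Treatment errors do not remove a patient from the response-rate analysis. Subset analyses that drop protocol deviators cannot support efficacy conclusions. These rules block the commonest exclusions of treated patients, but they do not create an all-randomised PFS set.
- *Allocation.* The stratification factors are collected at registration and a dose is sent back, so allocation probably happens then. This is a fair inference, though no date is required.
- *Little reason for unequal loss.* Eligibility documents are checked at registration, and the window to first dose is short against a 40-week median. Section 3.1.12 puts similar pregnancy-prevention conditions on the control arm: "All patients receiving cediranib alone must be counseled at a minimum of every 28 days about pregnancy precautions and risks of fetal exposure". This keeps the expected effect small.
- *Limited gain.* A non-starter censored on day 0 adds nothing to the logrank test, so the benefit depends on follow-up under 5.4.
- *Timing.* The documents do not show whether the analysis is still ahead.

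These points limit the severity. None supplies a randomisation time origin or a defined primary set.

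**Conclusion.** The concern holds and should be fixed. The plan permits departures from the as-randomised comparison; it does not demonstrate a bias. For non-starters the exclusion follows directly from the time origin. For ineligible patients it depends on how 13.5.2 is read.

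The effect is probably small, and its size and direction are unknown because no loss rates are given. Loss that is random, or proportional across arms, leaves the error rate essentially unchanged. Three losses from one arm, three to five times as likely among early failures, move it by about 1 point upward if from Arm B (to 11.7-11.9%) and by 1.3 to 2.3 points downward if from Arm A (to 9.4-8.4%). These figures assume exponential PFS, an unstratified test and assumed numbers lost. The sample size is not in error.

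**What to change.** For Phase II only:

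1. In 11.1.6, define PFS from the date of randomisation, and record that date as part of the 4.2 process.
2. In 13.1.2, state that the primary stratified logrank and Cox analyses include every randomised patient in the assigned arm, regardless of eligibility, treatment received or cancelled registration. Patients who withdraw or have no further assessments are censored at the last assessment.
3. In 13.5.2, state that the eligible-patient sentence does not govern primary PFS. State also that a cancelled registration does not by itself end 5.4 follow-up.
4. Report the eligible and treated sets as sensitivity analyses.

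Phase I can keep start of treatment as the origin, since PFS is a secondary objective there (section 1.1.2: "Determine the toxicity, duration of response, progression free survival, and overall survival in patients with DTC treated with cediranib plus lenalidomide"). If the analysis has already been done, the same rule should govern its reporting, with non-starters and ineligible patients accounted for by arm.

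The cost is wording, one recorded date, and some effort to obtain progression and survival status for non-starters who have not withdrawn. There is slight dilution: simulated power falls from 87.0% to 85.4% or 83.7% if 2% or 5% of Arm B have the control hazard. The planned 110 patients need not change.
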